## **2.4 Safety Objectives**

- to evaluate the safety of OPN-375 by monitoring AEs throughout the study; results of nasal examination, vital signs measurements (ie, blood pressure, pulse), and weight; and monitoring concomitant medication usage

## **2.5 Number of Subjects and Duration of Study**

The total planned number of subjects is approximately 333. Approximately 333 subjects will be randomly assigned to receive 1 of the 2 active treatments or placebo (111 subjects in each group); subjects will be randomized using a 1:1:1 ratio.

The expected participation period for a subject is approximately 26 weeks, including a pretreatment phase consisting of a Screening visit followed by a 7- to up to 21-day single-blind placebo run-in period and a 24-week double-blind treatment phase.

## **2.6 Termination of Study**

Premature termination of the trial may occur because of a regulatory authority decision, change in opinion of the Institutional Review Board (IRB)/Ethics Committee (EC), drug safety problems, or at the discretion of the Sponsor or their designee. If the study is prematurely terminated, the Sponsor or their designee will promptly notify the investigators.

### 3 STUDY DESIGN

#### 3.1 Study Overview

This is a 24-week, randomized, double-blind, placebo-controlled, parallel-group, multicenter study designed to assess the efficacy and safety of intranasal administration of OPN-375 (186 and 372 µg twice daily) in subjects with CRS with or without the presence of nasal polyps.

Subjects must sign an informed consent before any study-related procedure is performed. Subjects who meet eligibility criteria at Visit 1 (Screening) will enter a 7- to 21-day single-blind placebo run-in period to determine disease status and to ensure that they can comply with study procedures. At Visit 1 (Screening), nasoendoscopy-related (nasal examination and assessment of nasal cavity for presence of edema, polyps, or mucopurulence) procedures will be performed for all subjects. During the single-blind run-in period, subjects will administer morning and evening doses of the study drug (placebo) and will complete a daily diary (electronic) immediately before the morning and evening doses including recording of both instantaneous (evaluation of symptom severity immediately preceding the time of scoring) and reflective (evaluation of symptom severity over the past 12 hours) scores for nasal symptoms.

Subjects determined to meet diary eligibility criteria over a 7-day period during the first 14 days of the single-blind run-in period, will have a sinus computed tomography (CT) scan performed. The CT scan should be performed after diary eligibility is confirmed and prior to Day 21 of the screening run in period. CT scans performed prior to Day 21 and within 2 weeks prior to Visit 1, as part of routine clinical care, may be utilized if the scan meets the CT scan standards outlined in the Imaging Charter for this protocol. The resultant scan will be reviewed centrally to confirm study eligibility prior to randomization.

Those subjects meeting disease severity eligibility criteria (symptom severity and sinus opacification) will be randomly assigned through an interactive web response system (IWRS) to receive 1 of 2 active treatments or placebo: 186 or 372 µg of OPN-375 or placebo BID for the 24-week double-blind treatment phase. When the number of subjects with polyps reaches 50% of the total population, no additional subjects with polyps will be enrolled. During the first 12 weeks of the double-blind phase, electronic diaries will be completed twice daily by the subject to capture symptom scores for nasal congestion, nasal discharge, (anterior and/or posterior), facial pain or pressure sensation, and sense of smell, as well as use of approved rescue medication after the Week 4 visit. Subject-completed questionnaires will be used to measure the symptoms and social/emotional consequences of the subject's nasal disorder (SNOT- 22), health-related quality of life (EQ-5D, SF-36v2, and SF-6D), sleep quality and disturbances (PSQI), depressive symptoms (QID), work productivity, and objective smell test (SIT). Subjects will assess their global impression of change since starting the study drug using the PGIC scale. Health economic information related to CRS will also be collected (HPQ). Objective changes in disease severity will be assessed via sinus CT scan.

Safety will be assessed by monitoring of AEs, performing nasal examination, measuring vital signs (ie, blood pressure, pulse) and weight, and through collection of information for concomitant medications.

Refer to the [Schedule of Study Procedures and Evaluations](#), for the timing of all tests, procedures, and assessments that will be performed during the study.

A study flow diagram is shown in [Figure 3](#).

**Figure 3: Study Flow Diagram**

Single-blind Lead-In	Double-blind Treatment							End of Double-blind
Pretreatment	Randomization							
	<hr/> ----- 186 µg OPN-375 BID (n=111) ----- ----- 372 µg OPN-375 BID (n=111) ----- ----- Placebo BID (n=111) -----							
Visit 1 7 up to 21 days Screening /Run-in	Visit 2 Day 1 /Randomization /Baseline	Visit 3 Week 4	Visit 4 Week 8	Visit 5 Week 12	Subject Contact Week 16	Subject Contact Week 20	Visit 6 Week 24 /End of Double-blind /Early Termination	

BID=twice a day.

## 3.2 Endpoints

### 3.2.1 Efficacy Endpoints

#### 3.2.1.1 Primary Endpoint

##### Co-primary Endpoints

- change from baseline to the end of Week 4 in average total instantaneous AM scores (evaluation of symptom severity immediately preceding the time of scoring) of:
  - nasal congestion
  - nasal discharge (anterior and/or posterior)
  - facial pain/pressure sensation

The baseline CSNS is the average of the total instantaneous AM scores over the last 7 days of the single-blind run-in period, and the end of Week 4, scores are averaged over the 7 days before Week 4.

- change from baseline to Week 24/ET in the APOV in the ethmoid and maxillary sinuses

#### 3.2.1.2 Key Secondary Endpoints

- change from baseline to Week 4 on CSNS score in subjects from studies OPN-FLU-CS-3205 and OPN-FLU-CS-3206 who were symptomatic at trial entry despite reported use of an intranasal steroid for treatment of CRS within 30 days of Visit 1
- frequency of acute exacerbations of CRS over the 24-week treatment period, defined as a worsening of symptoms that requires escalation of treatment, from studies OPN-FLU-CS-3205 and OPN-FLU-CS-3206

### 3.2.1.3 Other Secondary Endpoints

- change from baseline to Weeks 4, 8, 12, and Week 24/ET in the SNOT-22 total and sub-domain scores for the total population and for the CRS with and without NP subgroups
- change from baseline in symptoms as measured by a CSNS: congestion, facial pain or pressure sensation, and nasal discharge (anterior and/or posterior) at the end of Week 4, 8, and 12 for the total population, for the CRS with NP and without NP sub-groups, and in patients with and without previous sinus surgery
- change from baseline to Weeks 4, 8, and 12 for the total population, for the CRS with NP and without NP sub-groups, and in patients with and without previous sinus surgery:
  - in average AM instantaneous (evaluation of symptom severity immediately preceding the time of scoring) and PM reflective (evaluation of symptom severity over the past 12 hours), averages are based on scores recorded in the diary for the 7 days before each time point for:
    - nasal congestion
    - sense of smell score
    - nasal discharge (anterior and/or posterior) score
    - facial pain or pressure sensation score
- change from baseline to Week 24/ET in the APOV in the ethmoid and maxillary sinuses for CRS with NP and without NP sub-groups and in patients with and without previous sinus surgery
- change from baseline to the Week 24/ET for CT related assessments:
  - Lund-Mackay Staging System total score, scores for ethmoids and maxillary sinuses combined, and scores for each sinus pair (eg, ethmoid, maxillaries, frontal, and sphenoid, and ostiomeatal complex)
  - percent of sinus volume occupied by disease in the worst maxillary sinus (WPOV-M), percent of sinus volume occupied by disease in the worst ethmoid sinus (WPOV-E), and percent of sinus volume occupied by disease in the worst sinus between maxillary and ethmoid sinuses (WPOV) for the total population, for the CRS with NP and without NP sub-groups, and in patients with and without previous sinus surgery
  - Zinreich modification of the Lund-Mackay Staging System total score, scores for ethmoids and maxillary sinuses combined, and for each sinus pair (eg, ethmoids, maxillary, frontal, and sphenoid)
  - Zinreich modification of the Lund-Mackay Staging System score for the worst sinus between maxillary and ethmoid sinuses in the total population and in subjects with NP and without NP sub-groups, and in subjects with and without previous sinus surgery
- time to first acute exacerbation of CRS, defined as a worsening of symptoms that requires escalation of treatment
- percent of subjects requiring rescue medication after Week 4

- change from baseline to Week 12 and Week 24/ET in the PSQI global and component scores
- percent of subjects indicating improvement on the PGIC at Week 4 and Week 24/ET
- severity of depression at Week 24/ET as measured by QIDS
- change from baseline to Week 24/ET for:
  - the MCS of the SF36v2
  - the PCS of the SF36v2
  - SF-36v2 individual domains
  - QIDS total score
  - SIT scores
  - EQ-5D VAS and dimensions
  - SF-6D derived scores
- comparison of health economic measures during the double-blind treatment phase related to CRS:
  - percent of subjects indicating that they are willing to consider sinus surgery at baseline and Week 24/ET
  - percent of subjects who meet the minimal objective criteria for surgical intervention (as defined in [Section 7.3](#)) at baseline and Week 24/ET
  - percent of subjects approved for surgery who no longer elect to undergo a surgery Week 24/ET
  - number and percentage of missed work days and the percentage of productive hours lost while at work from the HPQ
- change from baseline to Week 24/ET in SNOT-22 total score in subjects from both studies OPN-FLU-CS-3205 and OPN-FLU-CS-3206 who report using an intranasal, topically acting nasal steroid for the treatment of CRS within 30 days of Visit 1
- change from baseline to Week 24/ET the Global PSQI Score from studies OPN-FLU-CS-3205 and OPN-FLU-CS-3206

### **3.2.2 Safety Endpoints**

- assessment of safety through AEs, nasal examination, vital signs measurements, weight, and concomitant medication usage

## **3.3 Method of Treatment Assignment or Randomization**

Subjects will be randomly assigned to treatment according to a computer-generated randomization code. Randomization will be coordinated centrally through an IWRS. The system will provide subject identification numbers at Visit 1 (Screening), which are subsequently linked to the treatment assignments at randomization. Following completion of all baseline evaluations

on Day 1, subjects who meet all eligibility requirements will be randomly allocated to 1 of the 3 treatment groups using a 1:1:1 ratio:

- OPN-375 186 µg BID
- OPN-375 372 µg BID
- Placebo BID

Randomization will be stratified by presence of nasal polyps of grade 1 or larger at baseline (Present vs Absent) and previous sinus surgery (Yes vs No) (previous sinus surgery is defined as evidence of ethmoidectomy [partial or total], or maxillary antrostomy). A maximum of 189 Approximately 125 of the subjects without polyps will be randomized into the study . An IWRS will be used in this study to track enrollment, randomly assign subjects to treatment groups, and manage study drug supplies. At Visit 1 (Screening) and at each double-blind treatment phase study visit through Week 24, site staff will contact the IWRS and provide requested information to uniquely identify the subject. The IWRS will then provide the identifier (kit number) for the single-blind placebo kit at Visit 1 (Screening). The IWRS will then provide the identifier (kit number) for the double-blind study drug kit(s) to be dispensed at the respective double-blind visit.

### **3.4 Breaking the Blind**

This is a double-blind study. During the conduct of the study, the subject, investigator and study personnel at each center, and the Sponsor and/or its designated personnel directly involved in the clinical study will remain blinded to study treatment. The investigator will not be provided with the randomization code. The randomization codes will be maintained within the IWRS, which will allow the investigator to break the blind for an individual subject, if necessary. The investigator should contact the Sponsor or their designee to discuss individual situations before breaking the blind.

If a medical emergency occurs and a decision regarding the subject's condition/treatment requires knowledge of the treatment assignment, the study blind may be broken for the specific subject via the IWRS; the investigator will immediately notify the Medical Monitor of the situation. The date, time, and reason for unblinding must be documented in the source document and in the appropriate section of the case report form (CRF). Additionally, the documentation received from the IWRS indicating the code break must be retained, in a secure manner, in the subject's source documents.

## 4 SELECTION AND WITHDRAWAL OF SUBJECTS

### 4.1 Inclusion Criteria

Potential subjects must meet the following criteria to enter this study:

1. men or women aged 18 years and older at baseline visit
2. women of child bearing potential must be abstinent, or if sexually active:
  - a. be practicing an effective method of birth control (eg, prescription oral contraceptives, contraceptive injections, contraceptive patch, intrauterine device, double-barrier method [eg, condoms, diaphragm, or cervical cap with spermicidal foam, cream, or gel], or male partner sterilization) before entry and throughout the study, or
  - b. be surgically sterile (have had a hysterectomy or bilateral oophorectomy, tubal ligation, or otherwise be incapable of pregnancy), or
  - c. be postmenopausal (amenorrhea for at least 1 year).
3. women of child-bearing potential must have a negative urine pregnancy test at Visit 1 (Screening)
4. must have a history of CRS and be currently experiencing 2 or more of the following symptoms, one of which has to be either nasal congestion or nasal discharge (anterior and/or posterior nasal discharge) for equal to or greater than 12 weeks:
  - nasal congestion
  - nasal discharge (anterior and/or posterior nasal discharge)
  - facial pain or pressure
  - reduction or loss of smell
5. endoscopic evidence of nasal mucosal disease, with edema, purulent discharge, or polyps in middle meatus, bilaterally, or presence of bilateral disease on a prior CT scan performed within 14 days of Visit 1
6. must have confirmatory evidence via CT of bilateral sinus disease (have at least 1 sinus on each side of nose with a Lund-Mackay score of  $\geq 1$ )
7. baseline CT scan must show a combined  $\geq 25\%$  opacification of the ethmoid sinuses and  $\geq 25\%$  opacification of at least 1 maxillary sinus
8. must have at least moderate symptoms (as defined in [Section 7.2](#)) of nasal congestion as reported by the subject, on average, for the 7-day period preceding Visit 1 (Screening) run-in
9. must have an average morning score of at least 1.5 for congestion on the Nasal Symptom Scale (as defined in [Section 7.2](#)) recorded on the subject diary over a 7-day period during the first 14 days of the single-blind run-in period
10. must demonstrate an ability to correctly complete the daily diary during the run-in period to be eligible for randomization
11. Subjects with comorbid asthma or COPD must be stable with no exacerbations (eg, no emergency room visits, hospitalizations, or oral or parenteral steroid use) within the 3 months

before Visit 1 (Screening). Inhaled corticosteroid use must be limited to stable doses of no more than 1,000 µg/day of beclomethasone (or equivalent, see [Attachment 1](#)) for at least 3 months before Visit 1 (Screening) with plans to continue use throughout the study.

12. Subjects with aspirin-exacerbated respiratory disease, who have undergone aspirin desensitization and are receiving daily aspirin therapy, must be receiving therapy for at least 6 months prior to Visit 1.
13. must be able to cease treatment with intranasal steroids, inhaled corticosteroids (except permitted doses listed above for asthma and COPD) at the screening visit
14. must be able to cease treatment with oral and nasal decongestants and antihistamines at Visit 1 (Screening)
15. must be able to use the EDS correctly; all subjects will be required to demonstrate correct use of the practice EDS at Visit 1 (Screening), see [Section 6.1](#)
16. must be capable, in the opinion of the investigator, of providing informed consent to participate in the study. Subjects must sign an informed consent document indicating that they understand the purpose of and procedures required for the study and are willing to participate in the study.

#### **4.2 Exclusion Criteria**

Potential subjects who meet any of the following criteria will be excluded from entering this study:

1. women who are pregnant or lactating
2. inability to have each nasal cavity examined for any reason, including nasal septum deviation
3. inability to achieve bilateral nasal airflow
4. is currently taking XHANCE
5. have previously used XHANCE for more than 1 month and did not achieve an adequate symptomatic response
6. the nasal/sinus anatomy prevents the accurate assessment of sinus volume via CT scan
7. history of sinus or nasal surgery within 6 months before Visit 1 or has not healed from a prior sinus or nasal surgery
8. have current evidence of odontogenic sinusitis, sinus mucocele (the affected sinus is completely opacified and either the margins are expanded and/or thinned OR there are areas of complete bone resorption resulting in bony defect and extension of the “mass” into adjacent tissues), evidence of allergic fungal sinusitis, or evidence of complicated sinus disease (including, but not limited to, extension of inflammation outside of the sinuses and nasal cavity)
9. have a paranasal sinus or nasal tumor
10. have a polyp extending outside the OMC/middle turbinate (anterior or inferior) that is below the inferior turbinate attachment as determined by the nasoendoscopy at screening

11. have a nasal septum perforation
12. have had more than 1 episode of epistaxis with frank bleeding in the month before Visit 1 (Screening)
13. have evidence of significant mucosal injury, ulceration (eg, exposed cartilage) on Visit 1 (Screening) nasal examination/nasoendoscopy
14. have current, ongoing rhinitis medicamentosa (rebound rhinitis)
15. have significant oral structural abnormalities (eg, a cleft palate)
16. have a diagnosis of cystic fibrosis
17. history of eosinophilic granulomatosis with polyangiitis (Churg–Strauss syndrome) or dyskinetic ciliary syndromes
18. Symptom resolution or last dose of antibiotics for purulent nasal infection, acute sinusitis, or upper respiratory tract infection, influenza, or SARS-CoV-2 (COVID-19) has not occurred before Visit 1 or was less than 4 weeks before the CT scan. Potential subjects presenting with any of these infections may be rescreened 4 weeks after symptom resolution.
19. planned sinonasal surgery during the period of the study
20. allergy, hypersensitivity, or contraindication to corticosteroids or steroids
21. has used oral steroids in the past for treatment of CRS and did not experience any relief of symptoms
22. has a steroid eluting sinus stent still in place within 30 days of Visit 1
23. allergy or hypersensitivity to any excipients in study drug
24. exposure to any glucocorticoid treatment with potential for systemic effects (eg, oral, parenteral, intra-articular, or epidural steroids, high dose topical steroids) within 1 month before Visit 1 (Screening); except as noted in inclusion criteria for subjects with comorbid asthma or COPD
25. have nasal candidiasis
26. have history or current diagnosis of any form of glaucoma or ocular hypertension
27. history of IOP elevation on any form of steroid therapy
28. history or current diagnosis of the presence (in either eye) of a cataract unless both natural intraocular lenses have been removed
29. history of immunodeficiency
30. any serious or unstable concurrent disease, psychiatric disorder, or any significant condition that, in the opinion of the investigator could confound the results of the study or could interfere with the subject's participation or compliance in the study
31. have a positive drug screen or a recent (within 1 year of Visit 1 [Screening]) history of drug or alcohol abuse, or dependence that, in the opinion of the investigator could interfere with the subject's participation or compliance in the study
32. have participated in an investigational drug clinical trial within 30 days of Visit 1 (Screening)

33. have received mepolizumab (Nucala®), reslizumab (Cinquair®), dupilumab (Dupixent®), omalizumab (Xolair®), or benralizumab (Fasenra®) within 6 months of Visit 1 (Screening)
34. is using strong cytochrome P450 3A4 (CYP3A4) inhibitors (eg, ritonavir, atazanavir, clarithromycin, indinavir, itraconazole, nefazodone, neflifavir, saquinavir, ketoconazole, telithromycin, conivaptan, lopinavir, voriconazole, cobicistat)
35. is an employee of the investigator or study center, with direct involvement in the proposed study or other studies under the direction of that investigator or study center, or is a family member of the employee or the investigator
36. Patients who report unexplained worsening of vision within the past 3 months (e.g. difficulty reading or seeing traffic signs from a distance). A diagnosis of presbyopia established by an eye doctor is not exclusionary

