the data base. Site staff should follow-up with subjects as necessary to counsel them on completion of the electronic diaries. The site staff will evaluate the subject's severity scores, entered remotely into the electronic diaries, and will be notified when the subject meets eligibility criteria pertaining to their symptoms. When a subject reaches an average congestion severity score of at least 1.5 over a 7-day period during the first 14 days of the single-blind run-in period, they will be scheduled to have the CT scan to assess remaining eligibility requirements. The CT scan should be performed after diary eligibility is confirmed and prior to day 21 of the screening run in period. CT scans performed prior to Day 21 and within 2 weeks before Visit 1, as part of routine clinical care, may be utilized providing the scan meets the CT scan standards outlined in the Imaging Charter for this protocol.

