9.1.3 Baseline Value

Baseline is defined as the last measurement prior to receiving the first dose of double-blind treatment. For nasoendoscopy nasal examination, the assessment at Screening (Visit 1) will be used as the baseline assessment; for CT scan, the date of the procedure during the placebo run-in period will be considered the baseline visit. For all other procedures, the assessment at Visit 2 (Day 1) is considered the baseline assessment.

For the individual daily nasal symptom scores and CSNS, the 7-day average of the last 7 days in the run-in period immediately prior to randomization is considered the baseline value. Reference Section 9.3.1 and Table 9.1 above for further details.

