9.3.2 Quantitative (Volumetric) Measurement of CT Scan Image

The protocol for quantitative (volumetric) measurement of CT scan imaging is based on the Image Review Charter (IRC) – Revision C, (29 January 2020). Quantitative measurement of Sinus Volume and Opacification Volume will be performed by a trained analyst under the supervision of a Biomedical Engineer using a validated software system as described in the IRC.

The following quantitative variables are defined for each of the four sinuses: Maxillary (Left, Right), Ethmoid (Left, Right).

Sinus Volume (SV): the total volume of the specified sinus cavity regardless of the amount of mucosal inflammation that may be present. Total Sinus Volume will consist of both the soft tissue and air signal within the specified sinus. Sinus Volume will be reported in cubic millimeters.

Opacification Volume (OV): the total volume of the soft tissue and mucosal inflammation as visualized in the specified sinus. Opacification Volume will be reported in cubic millimeters.

Percentage of Opacified Volume (POV): $POV = OV/SV \cdot 100\%$

Missing Volumetric Measurements

Volumetric measurements (SV, OV) of a sinus may be missing due to technical issues that are unrelated to disease measurement; these measurements are reported as 'Unable to Assess.'

If the volumetric measurements in any sinus are missing at baseline, then the subject will be excluded from the FAS population. If either of the volumetric measurements in any sinus is missing at Week 24/ET, then the volumetric measurement for that sinus will be replaced by the baseline volumetric measurement.

Average Percentage of Opacified Volume (APOV)

APOV is the average percentage of opacified volume across both maxillary (L, R) and ethmoid (L, R) sinuses (all 4 sinuses) at each time point (Baseline, Week 24/ET). Larger values of APOV,

i.e., higher percentages of opacified volume, indicate greater severity of CRS; therefore, negative values for change from baseline APOV indicate improvement from baseline.

APOV-E is the average percentage of opacified volume in the ethmoid (L, R) sinuses at each time point (Baseline, Week 24/ET).

APOV-M is the average percentage of opacified volume in the maxillary (L, R) sinuses at each time point (Baseline, Week 24/ET).

Worst Percentage of Opacified Volume (WPOV)

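### Eligibility screens only anatomical obstacles to sinus measurement, yet one baseline sinus unreadable for a technical reason removes a randomised subject from every efficacy analysis

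*Protocol*

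**What the plan says.** **Eligibility.** The one measurability criterion in Protocol 4.2 is exclusion 6, which applies when "the nasal/sinus anatomy prevents the accurate assessment of sinus volume via CT scan". The CT inclusion criteria in Protocol 4.1 concern disease. Inclusion 6 asks that subjects "have at least 1 sinus on each side of nose with a Lund-Mackay score of" 1 or more, and inclusion 7 asks for a threshold in the combined ethmoids and for "opacification of at least 1 maxillary sinus" at the same level.

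**Timing.** Protocol 3.1 says of the baseline CT: "The resultant scan will be reviewed centrally to confirm study eligibility prior to randomization".

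**Endpoint.** APOV averages the percentage opacified over four sinuses, left and right maxillary and left and right ethmoid (Protocol 9.3.1, SAP 9.3.2).

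**Missing baseline volume.** SAP 9.3.2 says sinus volumes can be missing for technical reasons unrelated to disease, and then: "If the volumetric measurements in any sinus are missing at baseline, then the subject will be excluded from the FAS population". A sinus missing at Week 24/ET is handled differently: its baseline value is substituted and the subject stays in.

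**Missing baseline qualitative score.** SAP 9.3.6 uses the same FAS exclusion for a missing Zinreich-modified Lund-Mackay (ZLM) score in any sinus. Ten are scored, including frontal and sphenoid. The rule also covers the ostiomeatal complex score.

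**Analysis sets.** Protocol 9.2.3 and SAP 5.5 make the FAS the primary population for all efficacy analyses. For APOV, the protocol asks for at least one baseline measure and the SAP for a baseline measurement. Neither definition mentions the single-sinus exclusions.

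**The concern.** The eligibility rule and the analysis rule do not match. Eligibility asks whether anatomy prevents measurement; the SAP asks whether every sinus was in fact measured. A subject whose scan has one sinus unreadable for a technical reason falls between the two. Such a subject can pass the CT criteria, be randomised, receive 24 weeks of treatment and a second CT, and then contribute nothing to efficacy.

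The removal is also wider than its cause. CSNS comes from the diary and exacerbations from their own CRF, so an unreadable sinus says nothing about either. The per-protocol set and the observed-cases analysis are both drawn from the FAS, so neither recovers the subject. Under SAP 9.3.6 an unreadable frontal sinus, which plays no part in APOV, removes a subject whose APOV baseline is complete.

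At stake are power and randomised subjects who are exposed without being counted. The sample size section states no allowance for FAS loss.

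**Working it through.** **1. Can a subject reach randomisation and then be removed?**

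Take a subject whose ethmoids and right maxillary sinus are readable and diseased, with disease on both sides, and whose left maxillary sinus is unreadable for a technical reason.

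| Rule | Outcome |
|---|---|
| Inclusion 6: one scored sinus per side | met (an ethmoid on the left) |
| Inclusion 7: combined ethmoids and one maxillary sinus | met (right maxillary) |
| Exclusion 6: anatomy prevents measurement | not triggered (the cause is technical) |
| SAP 9.3.2: any of four volumes missing at baseline | out of the FAS |
| CSNS, APOV and exacerbation analyses | all lost |

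If instead only a frontal sinus is unreadable, all four APOV volumes are present, but SAP 9.3.6 still removes the subject.

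**2. The plan's own power figure**

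Inputs (Protocol 9.1, SAP 4.2): 111 per group, two-sided 5%, 88% power; CSNS difference 0.8 with SD 1.9; APOV difference 11.3 with SD 27.

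Standard error = SD × √(2/m); λ = difference / standard error; m is the number per group in the analysis.

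- CSNS: 1.9 × √(2/111) = 0.2550; λ = 0.8/0.2550 = 3.137. Normal approximation: Φ(3.137 − 1.960) = 88.0%. Noncentral t on 220 df: 87.8%.
- APOV: 27 × √(2/111) = 3.624; λ = 11.3/3.624 = 3.118. Normal approximation: Φ(3.118 − 1.960) = 87.7%. Noncentral t: 87.4%.

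The stated 88% is reproduced, with 111 as the number analysed per group rather than the number randomised.

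**3. Effect of losing a fraction f from the FAS**

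The documents give no rate, so f is assumed, with equal loss in each arm. m = 111(1 − f); power = P(|T| > t at 0.975 on 2m − 2 df), with T noncentral t with parameter λ. The last column is 111/(1 − f), rounded up.

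| f | Lost of 333 | m | λ CSNS | Power CSNS | λ APOV | Power APOV | Randomised per group to keep 111 |
|---|---|---|---|---|---|---|---|
| 0 | 0 | 111 | 3.137 | 87.8% | 3.118 | 87.4% | 111 |
| 1% | 3 | 109.9 | 3.121 | 87.4% | 3.102 | 87.1% | 113 |
| 3% | 10 | 107.7 | 3.089 | 86.8% | 3.071 | 86.4% | 115 |
| 5% | 17 | 105.5 | 3.057 | 86.1% | 3.039 | 85.7% | 117 |

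The cost is about 0.3 points at 1%, 1.0 at 3% and 1.7 at 5% for each endpoint.

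**The case against.** **The Imaging Charter may close the gap.** Scan standards and volumetric methods sit in a charter that is not supplied, and it may require rejection or repeat of an inadequate scan. This stands as a limit. In the protocol, however, the charter's standards are attached to reused routine-care scans, which "may be utilized if the scan meets the CT scan standards outlined in the Imaging Charter for this protocol", and no eligibility text says that all four sinuses must be readable.

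**The fault need not be visible in time.** A reader might infer that the central review would show an unreadable sinus before randomisation. The documents do not say so: Protocol 3.1 places the review before randomisation, but not the completion of four-sinus volumetry.

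**Inclusion 7 is not evidence of the gap.** It is tempting to read the one-maxillary-sinus requirement as accepting an unmeasured second one. It is a severity threshold: a maxillary sinus below it can be fully measurable. It matters only because it does not happen to close the gap.

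**Routine-care scans are not shut out.** Protocol 6.1 says that scans done "within 2 weeks before Visit 1, as part of routine clinical care, may be utilized", whereas SAP 9.1.3 says "for CT scan, the date of the procedure during the placebo run-in period will be considered the baseline visit". A reader might infer that subjects qualifying on an earlier scan have no APOV baseline and drop out of the FAS. SAP 9.1.3 first defines baseline as the last measurement before the first double-blind dose, which such a scan satisfies. SAP 3.1 repeats the routine-care allowance, and Protocol 6 treats the reused scan as the baseline CT. The clause merits at most an editorial clarification, and no loss should be projected from it.

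**The SAP was entitled to set the rule.** Protocol 9.3.3 leaves missing within-instrument data in the co-primary endpoints to the SAP. That supports having a rule for APOV. It does not explain removal from CSNS, or removal for a sinus outside APOV.

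**The effect is small.** It is, at low rates. In the exacerbation analysis, pooled with Study 3206, these subjects would also be a smaller share.

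**Conclusion.** The mismatch is in the text. Anatomical obstacles are screened before randomisation; technical ones are not, and a single unreadable baseline sinus costs the subject's data on every efficacy endpoint. The qualitative rule in SAP 9.3.6 widens this beyond the APOV sinuses, and neither FAS definition discloses it.

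The size is modest and conditional. With equal loss across arms, an assumed 1% to 5% takes power from 87.8% to 87.4%–86.1% for CSNS and from 87.4% to 87.1%–85.7% for APOV. The true rate is unknown and could be near zero if the charter already rejects such scans.

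A reader might go on to infer a biased comparison. The documents do not support that: the exclusion depends on a scan taken before randomisation, so provided reads are blinded it should not depend on treatment. The case for acting is that the loss is avoidable and cheap to prevent.

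**What to change.** 1. **Protocol, exclusion 6 and Section 6.1.** State that a subject is not randomised unless the central read before randomisation confirms that both maxillary and both ethmoid sinuses can be measured, whether the obstacle is anatomical or technical. Cost: one sentence in each place, a few more screen failures, and assessability to be confirmed within the existing run-in. By the time of this SAP both blinded interim analyses were done, so the change may reach few remaining subjects.

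2. **SAP 9.3.2 and 9.3.6, before unblinding.** For subjects already randomised, let an unreadable baseline sinus remove the subject only from the CT endpoints that use it. A missing maxillary or ethmoid volume would then affect APOV and the other volumetric endpoints that need it, and a missing frontal score only the qualitative scores that include it. CSNS and exacerbation data would be kept.

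3. **FAS definitions, Protocol 9.2.3 and SAP 5.5.** Reconcile both with item 2, since each now requires an APOV baseline for FAS membership. Cost: the two co-primary endpoints may be analysed on slightly different numbers, so report by arm how many subjects are left out of each CT endpoint and why.

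4. **SAP 9.1.3, editorial.** Say that the baseline CT is the qualifying scan accepted before randomisation, including a permitted routine-care scan.
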